5.3.1.2. Continuous Endpoints

Actual values (original unit and \log_{10} transformed values) and changes from baseline (\log_{10} transformed values) over time in HBsAg, HBV DNA and ALT (original unit) will be evaluated. Change from baseline is defined as follows: value at a given time point minus baseline value.

Changes in HBsAg (\log_{10} transformed values) from both EOT and Week 48 will be evaluated for the follow-up period.

The change from baseline value to the nadir (i.e. maximum decrease for each participant) in HBsAg and HBV DNA will be evaluated at three intervals: on-treatment nadir, during follow-up nadir, and entire study duration nadir.

5.3.1.3. Time to Event Endpoints

5.3.1.3.1. First HBsAg Seroclearance

Time to HBsAg seroclearance is defined as the number of days between the date of first study intervention intake and the date of the first occurrence of HBsAg seroclearance (i.e. the date of the first HBsAg seroclearance – the date of first study intervention intake + 1). The participants who withdrew early from the study before achieving HBsAg seroclearance or who did not achieve HBsAg seroclearance will be censored at the last available HBsAg assessment.

In addition, time to the first occurrence of the following events (i.e. the date of the first occurrence of the event – the date of first study intervention intake + 1) will be tabulated:

- HBsAg < 10 IU/mL
- HBsAg < 100 IU/mL
- HBsAg decline $\geq 1.0 \log_{10}$ IU/mL
- HBsAg decline $\geq 2.0 \log_{10}$ IU/mL
- HBsAg decline $\geq 3.0 \log_{10}$ IU/mL

These endpoints will also be analyzed considering participants who were re-treated with NA before achieving the endpoint as censored at the date of NA re-treatment.

5.3.1.3.2. Time to Flare

Time to biochemical flare (on- and off-treatment), clinical flare off-treatment, and virologic flare off-treatment will be evaluated.

Time to on-treatment flare will be defined as the number of days between the date of first study intervention intake and the date of the first occurrence of on-treatment flare (i.e. the date of the first on-treatment flare [the first of the two confirmation visits] of each type- the date of first study intervention intake+1). The participants who withdrew early from the study before experiencing on-treatment flare or who did not experience on-treatment flare will be censored at the last available blood markers or liver enzymes assessment at or before EOT.

Time to off-treatment flare will be defined as the number of days between the date of last study intervention intake and the date of the first occurrence of off-treatment flare (i.e. the date of experiencing the first off-treatment[the first of the two confirmation visits] flare of each type- the date of last study intervention intake). The participants who withdrew early from the study before experiencing off-treatment flare or who did not experience off-treatment flare will be censored at the last available blood markers or liver enzymes assessment.

5.3.1.3.3. Time to Virologic Breakthrough

Time to HBV virologic breakthrough will be defined as the number of days between the date of first study intervention intake and the date of the first occurrence of virologic breakthrough (i.e. the date of the first virologic breakthrough [the first of the two confirmation visits] - the date of first study intervention intake +1). The participants who withdrew early from the study before experiencing virologic breakthrough or who did not experience virologic breakthrough will be censored at the last available HBV DNA assessment at or before EOT.

5.3.1.4. Endpoints for Correlation

Correlations between baseline characteristics, and on-treatment HBV blood markers and/or their change from baseline at Week 24 and 48 with off-treatment endpoints will be evaluated. The list of HBV blood markers, including but not limited to, are defined below:

Off treatment HBV marker	Baseline Characteristics/On treatment HBV marker
HBsAg change from baseline at FU Week 12	
 • Age • Baseline NA treatment duration • HBsAg value at baseline • HBsAg change from baseline at Week 24 • HBsAg change from baseline at Week 48
HBsAg change from baseline at FU Week 24	
 • Age • Baseline NA treatment duration • HBsAg value at baseline • HBsAg change from baseline at Week 24 • HBsAg change from baseline at Week 48
HBsAg change from baseline at FU Week 48	
 • Age

Off treatment HBV marker	Baseline Characteristics/On treatment HBV marker
	
 • Baseline NA treatment duration • HBsAg value at baseline • HBsAg change from baseline at Week 24 • HBsAg change from baseline at Week 48
HBsAg seroclearance at FU week 24 (Yes;No)	
 • Age • Baseline NA treatment duration • HBsAg value at baseline • HBsAg change from baseline at Week 48 • HBsAg value at Week 48 • HBsAg seroclearance at week 24 (Yes;No) • HBsAg seroclearance at week 48 (Yes;No) • Anti-HBe antibodies status at week 48 (Positive:Negative)
HBsAg seroclearance at FU week 48 (Yes;No)	
 • Age • Baseline NA treatment duration • HBsAg value at baseline • HBsAg change from baseline at Week 48 • HBsAg value at Week 48 • HBsAg seroclearance at week 24 (Yes;No) • HBsAg seroclearance at week 48 (Yes;No) • Anti-HBe antibodies status at week 48 (Positive:Negative)
Partial cure (Yes;No) at FU Week 24 (Yes;No)	
 • Age • Baseline NA treatment duration • HBsAg value at baseline • HBsAg value at Week 48 • HBsAg seroclearance at week 24 (Yes;No) • HBsAg seroclearance at week 48 (Yes;No) • Anti-HBe antibodies status at week 48 (Positive:Negative)
Partial cure (Yes;No) at FU Week 48 (Yes;No)	
 • Age • Baseline NA treatment duration • HBsAg value at baseline • HBsAg value at Week 48 • HBsAg seroclearance at week 24 (Yes;No) • HBsAg seroclearance at week 48 (Yes;No) • Anti-HBe antibodies status at week 48 (Positive:Negative)
Treatment failure at FU Week 24 (Yes;No)	
 • Age • Baseline NA treatment duration • HBsAg value at baseline • HBsAg value at Week 48 • HBsAg seroclearance at week 24 (Yes;No) • HBsAg seroclearance at week 48 (Yes;No) • Anti-HBe antibodies status at week 48 (Positive:Negative)
Treatment failure at FU Week 48 (Yes;No)	
 • Age • Baseline NA treatment duration • HBsAg value at baseline • HBsAg value at Week 48 • HBsAg seroclearance at week 24 (Yes;No) • HBsAg seroclearance at week 48 (Yes;No) • Anti-HBe antibodies status at week 48 (Positive:Negative)

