1.2. Trial Design

This is a Phase 2b, multicenter, randomized, double-blind, placebo-controlled, 2-arm parallel-group study to evaluate the efficacy of 48-week study intervention with a JNJ-3989+JNJ-6379+NA regimen compared to NA treatment alone, assessed by HBsAg seroclearance at Week 72 (ie, 24 weeks after completion of all study interventions at Week 48) without restarting NA treatment in HBeAg-negative virologically suppressed CHB-infected

participants who received NA treatment for at least 2 years prior to screening. All participants will stop all study interventions including NAs at Week 48 and will be followed up until Week 96. After completing this study, participants may have the option to enroll into a long-term follow-up study.

A target of 120 HBeAg-negative virologically suppressed CHB-infected male and female participants, 18-65 years (inclusive) of age, who received NA treatment for at least 2 years prior to screening will be randomized in a 2:1 ratio to one of the following intervention arms:

- Arm 1 (N=80): 200 mg JNJ-3989 + 250 mg JNJ-6379 + NA
- Arm 2 (N=40): Placebo + Placebo + NA

NA treatment refers to entecavir (ETV), or tenofovir disoproxil fumarate (TDF), or tenofovir alafenamide (TAF).

The study will be conducted in the following phases:

- **Screening phase:** 4 weeks. If necessary, eg, for operational reasons, the screening phase may be extended up to a maximum of 6 weeks on a case-by-case basis and in agreement with the sponsor.
- **Double-blind study intervention phase:** from Day 1 (ie, baseline) up to Week 48. All participants who complete 48-week study intervention should stop all study interventions including NAs at Week 48.
- **Follow-up phase:** for 48 weeks after the end of investigational intervention.

An Independent Data Monitoring Committee (IDMC) was commissioned for this study to monitor and review data in an unblinded manner on a regular basis to ensure the continuing safety of the study participants. The committee will meet periodically to review unblinded data, as well as the efficacy and safety results from the interim analyses (IAs) at prespecified time points (see Section 3). A separate IDMC SAP describes details of the safety and efficacy analyses included in the IDMC periodical data reviews.

In addition, an independent Flare Expert Panel (iFLEP) was appointed for flares monitoring and adjudication. Details on the IDMC and iFLEP activities are described in their respective charter.

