5.3.2.4. Endpoints for Correlation

Correlations will be evaluated graphically with scatter plots and heat maps displaying such potential associations by intervention arm and/or selected subgroups (baseline NA treatment duration, age, and baseline HBsAg).

The following correlation coefficients will be calculated by study intervention arm for the different correlation scenarios:

- Pearson's correlation coefficient for two continuous variables.
- Phi correlation coefficient for two binary variables.
- Point biserial correlation coefficient for one binary variable and one continuous variable.

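### Nine of the planned HBsAg marker correlations share the same baseline measurement on both sides, so their no-relation value is generally not zero

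*SAP*

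**What the plan says.** SAP 5.3.1.4 lists off-treatment outcomes with the markers each is to be correlated with. Three outcomes are change scores: "HBsAg change from baseline at FU Week 12" and the same change at follow-up Weeks 24 and 48. Each is paired with age, NA treatment duration, "HBsAg value at baseline", "HBsAg change from baseline at Week 24" and "HBsAg change from baseline at Week 48". SAP 5.3.1.2 fixes the meaning of change: "Change from baseline is defined as follows: value at a given time point minus baseline value", with HBsAg changes on the log10 scale.

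SAP 5.3.2.4 provides scatter plots and heat maps, and adds: "The following correlation coefficients will be calculated by study intervention arm for the different correlation scenarios". For these pairs that is Pearson's "correlation coefficient for two continuous variables". The section names no partial correlation, no baseline-adjusted model and no reference value other than zero. The planned arm sizes in SAP 1.2 are 80 ("Arm 1 (N=80): 200 mg JNJ-3989 + 250 mg JNJ-6379 + NA") and 40 (placebo plus NA).

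The correlations are the listed endpoint for a secondary objective in SAP 1.1: finding baseline and on-treatment markers of sustained off-treatment response.

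**The concern.** Write X for baseline and Y for a later value. The outcome is Y - X. Its listed predictors include X itself and two other differences that subtract the same X. Visit-to-visit noise in X enters both sides. A participant whose Day 1 value happens to be high shows a larger apparent fall at every later visit, with no biology involved.

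A reader of a heat map takes zero as the value meaning no relation. For these pairs zero is in general not that value, and the raw coefficient does not show how far away it lies. Baseline HBsAg and on-treatment decline could look like markers of off-treatment decline when they are not. The direction can also mislead. A negative coefficient reads as higher baseline going with larger decline, whereas Protocol 2.1 cites lower baseline HBsAg as the predictor of off-therapy seroclearance. The change-score rows could then seem to contradict the seroclearance rows of the same table for arithmetic reasons alone.

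**Working it through.** **Which pairs.** Change outcomes 3 x 5 = 15; seroclearance 2 x 8 = 16; partial cure 2 x 7 = 14; treatment failure 2 x 7 = 14. The total is 59. Pairs with a shared subtracted baseline: 3 outcomes x 3 predictors = 9.

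**Inputs.** The definition of change, the statistic and the arm sizes come from the SAP. The documents give no SD, between-visit correlation or reliability for HBsAg, so those are assumptions shown as ranges. The plan states no figure to reproduce.

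**Change against baseline.** With rho = corr(X, Y) and k = SD(Y)/SD(X):

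corr(Y - X, X) = (rho·k - 1) / sqrt(1 + k² - 2·rho·k)

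With k = 1 this is -sqrt((1 - rho)/2):

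| rho | r |
|---|---|
| 0.5 | -0.50 |
| 0.7 | -0.39 |
| 0.9 | -0.22 |
| 0.99 | -0.07 |

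It is zero only when rho·k = 1, for example rho = 0.8 with k = 1.25. At rho = 0.7 and k = 1.5 it is +0.05.

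**Change against change.** With equal SDs and equal pairwise correlations, corr(Y1 - X, Y2 - X) = +0.50 for any rho below 1. A stable personal level plus independent visit noise gives this pattern.

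**Allowing true change to vary.** Let the true level have variance VT, true changes variance VD (independent of level and of each other), and visit noise variance Ve:

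- change against baseline: -Ve / sqrt((VT + Ve)(VD + 2Ve))
- change against change: Ve / (VD + 2Ve)

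With assumed SDs of 0.6 log10 for level and 0.5 log10 for true change:

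| Noise SD (log10) | Change vs baseline | Change vs change |
|---|---|---|
| 0.1 | -0.03 | +0.04 |
| 0.2 | -0.11 | +0.12 |
| 0.3 | -0.21 | +0.21 |

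**Scale.** The two-sided 90% limit on |r| around zero is 0.26 at n = 40 and 0.19 at n = 80. In 10,000 simulated trials with equal SDs and rho = 0.7, change against baseline passed it in 80% (n = 40) and 98% (n = 80). Change against change passed it in 96% and over 99%.

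**Units.** SAP 5.3.1.4 does not say whether the baseline value is in IU/mL or log10. In IU/mL (assumed log10 SD 0.6, equal-SD model) the change-against-baseline value shrinks, to about -0.16 or -0.17 at rho = 0.9, but remains.

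**Does adjusting for baseline remove it?** No. Regressing Y instead of Y - X on X adds exactly 1 to the slope and leaves the residuals unchanged. For change against change, the baseline-partialled correlation under a stable level plus noise is rho/(1 + rho): 0.47 at rho = 0.9, against 0.50 unadjusted. In the varying-change model with noise SD 0.3, VT = 0.36, VD = 0.25 and Ve = 0.09. The conditional covariance is 0.36 - 0.36²/0.45 = 0.072 and the conditional variance is 0.70 - 0.288 = 0.412. The partial correlation is 0.072/0.412, about 0.17, against 0.21 unadjusted. What remains is real prediction of the follow-up level, because a second reading helps locate a noisy personal level. It is not prediction of change.

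**Does the screening value remove it?** Let S be screening HBsAg, the true level plus its own independent noise. Then Y - X is true change plus the noise at follow-up and at Day 1, none of which is in S. So corr(Y - X, S) = 0. In the same way corr(Y2 - X, Y1 - S) = 0 when the true changes are independent. A simulation of the same noise models gave values within 0.001 of zero.

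**The case against.** The strongest reply concerns reach. Fifty of the 59 pairs are not coupled, including all 44 in the six binary rows (seroclearance, partial cure and treatment failure at follow-up Weeks 24 and 48). Those rows express response most directly, and they already use baseline HBsAg and the Week 48 HBsAg value. Functional cure is also modelled on screening HBsAg level and on baseline HBsAg subgroups (SAP 5.2.4), and the time-to-event models take selected baseline factors (SAP 5.3.2.3). No test, interval or decision rule is attached to the coefficients. All of this stands, and it limits the point to how nine descriptive numbers are read. None of these other analyses corrects the nine coefficients. The repeated-measures model in SAP 5.3.2.2.1 includes a baseline term but serves the arm comparison.

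The second reply concerns size. Equal SDs with low rho means that much of the spread in log10 HBsAg is visit noise, and no document supports that. If active treatment widens the follow-up spread, k above 1 is plausible in Arm 1, and the coefficient could be near zero or positive. This also stands. A reader might infer that -0.5 and +0.5 are expected sizes, or that the sign is always negative against baseline. The documents support neither, since they give no rho, SD or reliability.

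**Conclusion.** The point holds for nine of 59 pairs. As written, their Pearson coefficients have a no-relation value that is generally not zero, and nothing in the SAP corrects or flags this. Under the assumed noise models the offset is about -0.03 to -0.5 for change against baseline and +0.04 to +0.5 for change against change. The small ends need widely varying true change and low noise; the large ends need little true change, and against baseline also heavy noise. The problem is probably worse in the control arm if true change there is small relative to noise, which is again an assumption.

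A reader might go further and conclude that the marker objective as a whole is undermined. The documents do not support that: the binary-response rows carry no shared term, the coefficients are descriptive, and the primary analysis does not use them. The change is worth making because it is cheap and the raw coefficient cannot show which case applies.

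**What to change.** Amend SAP 5.3.1.4 and 5.3.2.4 for these nine pairs only.

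1. Use log10 HBsAg at follow-up Weeks 12, 24 and 48 as the outcome. Report by arm its association with log10 baseline HBsAg and, adjusted for baseline, with the Week 24 or Week 48 value. State that this is prediction of the follow-up level, not of change.
2. If change is kept as the outcome, break the shared term with the quantitative screening HBsAg, which the schedule in Protocol 1.3.1 already collects alongside Day 1. Use it as the predictor in place of baseline, or as the reference for the on-treatment change. Either gives zero under the no-relation models above, provided that screening and Day 1 noise are independent.
3. If the raw coefficients and plots stay, label them as descriptive and sharing a baseline term. State the scale of the baseline value.

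The cost is SAP wording and slightly more analysis, with no new samples or visits. Option 2 needs both values. Under SAP 2.2 a missing Day 1 result is replaced by the last earlier one, which could be the screening value and would bring the shared term back, so such participants should be left out of it.

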5.3.2. Analysis Methods

Statistical comparisons of all secondary endpoints between intervention arms will be done with no adjustment for multiplicity.

5.3.2.1. Binary Endpoints

The number and proportion (%) of participants achieving the endpoints defined in Section 5.3.1.1 will be summarized. The associated 90% CI may also be included.

The following binary endpoints will be compared between treatment arms using a 2-sided 90% CI of the difference in proportions between the treatment groups (Arm 1 minus Arm 2) that will be constructed using a Mantel-Haenszel test controlling for stratification factors, i.e., HBsAg level (<1,000 IU/mL or \geq 1,000 IU/mL), race (Asian versus non-Asian) and type of NA (TDF/TAF versus ETV):

- HBsAg seroclearance:
 - at Week 48
 - at Week 96 (ie, 48 weeks after completion of all study interventions at Week 48) without restarting NA treatment,
 - 24 weeks after stopping all study interventions (regardless when intervention was stopped) without restarting NA treatment, and
 - 48 weeks after stopping all study interventions (regardless when intervention was stopped) without restarting NA treatment

Bar charts will be provided for selected endpoints for proportions (%) in each intervention arm.

Cumulative percentage of participants achieving any given decrease from baseline at Week 72 and Week 96 in HBsAg and HBV DNA (Section 5.3.1.1.5) will be presented graphically.

Subsections below describe the additional analyses planned for only those specific other secondary binary endpoints that require further evaluations.

5.3.2.1.1. Suppressed HBV DNA

The number of occurrences each subject has HBV DNA <LLOQ will be determined and summarized by intervention arm using frequency distributions and descriptive statistics. Additionally, the number of occurrences will be displayed graphically.

5.3.2.1.2. HBsAg Seroconversion

For all participants achieving HBsAg seroconversion, descriptive statistics will be calculated for the level of anti-HBs antibodies at the timepoint when achieving the HBsAg seroconversion by intervention arm. In an additional summary, the level of anti-HBs antibodies at the specific timepoint (i.e. Week 48, Week 72, Week 96) will be summarized for the subset of the participants achieving HBsAg seroconversion at any time before or at that given timepoint by intervention arm.

In addition, the number and proportion of participants with appearance of anti-HBs antibodies and without seroclearance of HBsAg will also be summarized by intervention arm and analysis phase.

5.3.2.1.3. Flares

The incidence rate will be calculated and summarized for each type of on-treatment or off-treatment flares (virologic, biochemical and clinical) separately, as well as the overall incidence of participants experiencing at least one flare, regardless of type, by study intervention arm. Additionally, for each participant the total number of flares the participant experienced will be counted by type. Such counts will be used to summarize the distribution of the total number of flares by type and by intervention arm.

For on-treatment biochemical flares, the incidence of flares causing treatment discontinuation will be summarized by intervention arm. Further, for off-treatment flares, the count and percentage of participants who experienced a flare followed by NA re-treatment will be summarized by flare type and intervention arm. Similarly, the incidence of flares followed by the achievement of HBsAg seroclearance (at any time) will be summarized by flare type and intervention arm.

For off-treatment virologic, biochemical and clinical flares, the count and percentage of participants who experienced a flare will be summarized by intervention arm and selected subgroups (i.e. by NA type at study entry, by HBsAg levels at EOT, by HBcrAg levels at EOT). Biochemical flares will also be summarized in the follow-up after NA re-treatment. The cut-offs for HBsAg and HBcrAg levels at EOT are provided in Sections 5.3.1.1.5 and 5.4.1.1.2.

Flares that are associated with signs of liver decompensation will be provided in a listing.

5.3.2.1.4. NA Re-Treatment Criteria During Follow-Up

A cross-tabulation of participants who actually re-started NA treatment (re-started/not restarted) versus participants who met the above criteria (met/not met) will be presented over time.

5.3.2.2. Continuous Endpoints

Descriptive statistics on actual values (original unit and \log_{10} transformed values) and changes from baseline (\log_{10} transformed values) over time in HBsAg, HBV DNA, and ALT (original unit) will be summarized by intervention arm. Mean (+/- SE) plots of the actual values and the change from baseline (\log_{10} transformed) will be presented over time per endpoint by intervention arm.

Subsections below describe the additional analyses planned for only those specific secondary endpoints that require further evaluations.

5.3.2.2.1. HBsAg and HBV DNA

The change from baseline value to the nadirs (i.e. maximum decrease for each participant) in HBsAg and HBV DNA will be summarized descriptively by intervention arm. Box plots of the changes to nadirs in HBsAg and HBV DNA will display the distribution by intervention arm.

Change from baseline based on \log_{10} transform for quantitative HBsAg and HBV DNA will be analyzed using mixed effects model for repeated measures [MMRM]) including intervention arm, analysis time point (week), their interaction, and 3 randomization stratification factors (screening HBsAg level [$<1,000$ IU/mL or $\geq 1,000$ IU/mL], race [Asian versus non-Asian] and type of NA [TDF/TAF versus ETV]) and baseline blood marker categorical variable as fixed effects. In addition, the above model will be augmented with an intervention arm-by-analysis week interaction term (i.e. treatment-by-time interaction term) to evaluate the change of treatment effect over time and the intervention arm-by-baseline interaction term. The covariance structure will include a random intercept at the level of the participant to capture between-participant variability, while within-participant variability will be captured with an unstructured (type=UN) covariance matrix. In case of convergence problems, simpler variance-covariance structures such as Toeplitz or AR (1) will be considered. The selection of any of these structures will be determined after exploration of the observed correlation structure. The LS mean of change from baseline, standard error (SE), 90% confidence interval (CI) and p-values will be provided.

Descriptive statistics on actual values (original unit and \log_{10} transformed values) and changes from baseline (\log_{10} transformed values) at end of treatment in HBsAg and HBV DNA will be summarized by study intervention arm by outcome response (i.e. by functional cure status at Week 72, and by partial cure status at Week 72).

Spaghetti plots for both absolute values and changes from baseline of HBsAg and HBV DNA will be presented over time per blood marker by intervention arm and by selected subgroups (e.g. HBV Genotype) and by outcome response (i.e. by functional cure status at Week 72, and by partial cure status at Week 72).

Cross-tabulations overtime and overall of quantitative versus qualitative HBsAg values will also be presented.

Shift tables in HBV DNA categories from baseline will also be summarized by study intervention arm.

Waterfall plots for changes from baseline of HBsAg, and HBV DNA will also be presented.

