2.1.3. Analysis Visits and Time Points

All visits for all assessments (safety, efficacy or PK) will be uniquely allocated within each phase to an analysis time point based on the analysis relative day (ADY) compared with the target day based on [Table 2](#). All assignments will be made in chronological order. Once a visit is assigned to a visit window (Time interval in [Table 2](#)), it will no longer be used for a later time point except for the end of treatment (EOT) and the end of study (EOS) visits. If two or more visits fall within the same interval in the same phase, only one measurement will be selected for the analysis time point per phase in order to have only one evaluation per participant. The following rules will be applied:

1. The measurement closest to the target day in that phase will be used.
2. If the measurements fall equidistant from the target day, the last measurement in chronological order within the interval will be used per phase.
3. If there are two or more measurements on the same day, then the last measurement in chronological order will be used. If the time of the assessment is not available the highest record/sequence number will be selected.

The listings will include all measurements, also those multiple assessments within the same visit window/phase.

End of treatment (i.e. EOT) and end of study (i.e. EOS) time points will be included in all analysis over time unless stated otherwise.

Note: For the selection of the patient-reported outcome (PRO) measurements the above algorithm needs to be performed on the entire questionnaire (filled in at a specific date and time) and not on the individual questions /items (i.e., not mixing answers from different questionnaires)

Table 2 provides the analysis time points, time intervals for each visit per analysis phase.

Table 2: Analysis Time Point and Time Intervals by Analysis Phase

Analysis phase	DB Target day	Analysis time point (Week)	Analysis time point (label)	Time interval (DB days)
Screening	$-\infty$	-1	Screening	<0
Double-blind Study intervention	1	0	Baseline	Pre-dose: 1
	15	2	Week 2	[2, 22]
	29	4	Week 4	[23, 43]
	57	8	Week 8	[44, 71]
	85	12	Week 12	[72, 99]
	113	16	Week 16	[100, 127]
	141	20	Week 20	[128, 155]
	169	24	Week 24	[156, 183]
	197	28	Week 28	[184, 211]
	225	32	Week 32	[212, 239]
	253	36	Week 36	[240, 267]
	281	40	Week 40	[268, 295]
	309	44	Week 44	[296, 323]
	337	48	Week 48	[324, 350]
	last visit in double-blind phase	49*	EOT	

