Table 2: Analysis Time Point and Time Intervals by Analysis Phase

Follow-up	FU Target day	Analysis time point (Week)	Analysis time point (label)	Time interval (FU days)
	15	50	Follow-up Week 2	[1, 22]
	29	52	Follow-up Week 4	[23, 43]
	57	56	Follow-up Week 8	[44, 71]
	85	60	Follow-up Week 12	[72, 99]
	113	64	Follow-up Week 16	[100, 127]
	141	68	Follow-up Week 20	[128, 155]
	169	72	Follow-up Week 24	[156, 190]
	197	76	Follow-up Week 28**	[191, 204]
	211	78	Follow-up Week 30	[205, 218]
	225	80	Follow-up Week 32**	[219, 232]
	253	84	Follow-up Week 36	[233, 274]
	281	88	Follow-up Week 40**	[275, 288]
	295	90	Follow-up Week 42	[289, 302]
	309	92	Follow-up Week 44**	[303, 316]
	337	96	Follow-up Week 48	[317, $+\infty$]
	last visit in the study	999*	EOS	

*End of treatment (EOT) visit will be the last post-baseline visit in double-blind phase, and End of study (EOS) visit (last available data during the follow-up) will be the last visit in the study.

** Visits at Follow-up Weeks 28, 32, 40, and 44 were added to the study with Protocol Amendment 3 (finalized on 30 September 2021) to allow more frequent monitoring of NA re-treatment criteria. Consequently, the time intervals for Follow-up Weeks 30 and 42 have been shortened to create space for the new visits.

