5. EFFICACY

All efficacy data will be analyzed by intervention arm, analysis phase and over time (when applicable). The primary analysis set will be the mITT analysis set (see definition in Section 2.3). Selected efficacy endpoints will be also analyzed using the ITT and PP analysis sets, respectively (see definition in Section 2.3). Efficacy assessments over time will be performed at the analysis time points defined in Section 2.1.

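### The HBsAg/HBV DNA MMRM does not exclude the derived EOT and EOS time points, so as written each participant's last double-blind and last study values enter twice

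*SAP*

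**What the plan says.** SAP 5.3.2.2.1 analyses log10 change from baseline in HBsAg and HBV DNA with a "mixed effects model for repeated measures [MMRM]) including intervention arm, analysis time point (week), their interaction", plus the stratification factors and baseline. On the covariance it says "The covariance structure will include a random intercept at the level of the participant", and that "within-participant variability will be captured with an unstructured (type=UN) covariance matrix". Toeplitz or AR(1) may be substituted if the model does not converge. The section lists no visits, does not say whether one phase or both are modelled, and excludes no time point.

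The time factor has the same name as a column of Table 2 in SAP 2.1.3. That column holds the scheduled weeks and two derived entries, EOT as 49 and EOS as 999. The accompanying rules are:

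- "End of treatment (i.e. EOT) and end of study (i.e. EOS) time points will be included in all analysis over time unless stated otherwise".
- Once a visit has been assigned to a window, "it will no longer be used for a later time point except for the end of treatment (EOT) and the end of study (EOS) visits".
- "End of treatment (EOT) visit will be the last post-baseline visit in double-blind phase".
- "End of study (EOS) visit (last available data during the follow-up) will be the last visit in the study".

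SAP 5 links these to efficacy: "Efficacy assessments over time will be performed at the analysis time points defined in Section 2.1".

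Two other places bear on the point. SAP 5.3 puts the major secondary endpoints on an observed-case basis. SAP 5.3.1.1.1 limits carry-forward where it is intended: nothing before Week 40 may stand in for Week 48, and nothing more than 12 weeks earlier for Week 96.

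**The concern.** EOT and EOS are not new measurements. For a completer, EOT is normally the Week 48 record and EOS the Follow-up Week 48 record. For someone who left early, they are the last available values, however old, relabelled and placed at the end of the double-blind phase or of the study. In a descriptive table this is harmless. In a repeated-measures model with time as a factor it does two things.

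1. It adds a column that duplicates another, which an unstructured covariance cannot accommodate.
2. It gives the model an apparent observation next to the missing Week 48 or Week 96. The estimate at that visit then leans on the carried value rather than on the missing-at-random prediction from the participant's trajectory.

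At stake are the LS means, 90% CIs and p-values that this section promises for two main secondary markers.

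**Working it through.** **Plan's own figure.** The plan gives no figure for this model. Its only power statement (above 91%, primary Mantel-Haenszel test, 80 versus 40, 25% versus 5%, one-sided 0.05) is reproduced at 91.7% by exact enumeration of the unstratified test. Nothing below depends on it.

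**Time points.** Table 2 has 13 post-baseline double-blind and 15 follow-up time points, 28 in all, or 30 with EOT and EOS. An unstructured matrix has T(T+1)/2 parameters: 28×29/2 = 406, or 30×31/2 = 465, for 120 participants. For the double-blind phase alone it is 13×14/2 = 91, or 14×15/2 = 105 with EOT.

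**Unstructured covariance.** The documents give no SD, correlation or dropout, so all of these are assumed:

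- 80:40 participants; Weeks 4, 12, 24, 36 and 48.
- Active mean −2.0(1 − e^(−week/16)); control mean −0.05×week/48. The true Week 48 difference is −2(1 − e^(−3)) + 0.05 = −1.850.
- Covariance 0.15 + 0.10×min(s,t)/48, plus 0.01 on the diagonal. Withdrawal is unrelated to outcome.

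In one simulated trial with 9 of 120 withdrawn:

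- Scheduled visits only: smallest eigenvalue 0.0116, condition number 76, log-likelihood converges at 600.4.
- EOT added: the completers' covariance has rank 5 of 6, the fitted Week 48–EOT correlation is 1.0, and the smallest eigenvalue is zero to machine precision. As the EOT-specific variance falls from 1e-1 to 1e-10, the log-likelihood rises from 732.0 to 1880.5 without a maximum. Each 100-fold fall adds ½ ln(100) per completer: 111 × 2.3026 = 255.6, which matches 1880.5 − 1624.9.
- If 5% to 10% of participants have an EOT value that differs from their last scheduled value: correlation 0.999, condition number about 2,900. The matrix is near-singular, not singular.

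**Why the Week 48 estimate becomes LOCF.** With correlation 1 and equal variances, a withdrawn participant's predicted Week 48 value is μ48 + (EOT − μEOT). Averaging over an arm of n with w withdrawn gives μ48 = μEOT + (w/n)(μ48 − μEOT), so μ48 = μEOT, the LOCF mean. Averages over 12 simulated trials agree:

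| Withdrawal | Scheduled visits only | With EOT | Shift |
|---|---|---|---|
| 5% | −1.823 | −1.790 | +0.033 |
| 10% | −1.853 | −1.777 | +0.076 |
| 20% | −1.835 | −1.716 | +0.119 |

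The shift is toward zero, against the active arm.

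**AR(1) fallback, both phases.** Assumed: 80:40, 13 + 13 visits, intercept SD 0.3, AR(1) error SD 0.4, rho 0.9. In the rebound scenario, active-arm HBsAg returns to about −0.8 log10 by Week 96, with a true difference of −0.60. Three runs of 120 to 300 replicates gave, at Week 96:

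| Profile | Loss active/control | Bias with EOT/EOS | 90% CI coverage with | Coverage without |
|---|---|---|---|---|
| Rebound | 15%/5% | −0.06, −0.08, −0.08 | 82%, 79%, 82.5% | 87%, 91%, – |
| Rebound | 25%/15% | −0.12, −0.13, −0.13 | 68%, 66%, 63% | 86%, 91%, – |
| Rebound | 10%/10% | −0.05 | 81% | 86% |
| Rebound | 5%/5% | −0.01, −0.03 | 89%, 89.5% | 89%, 90.5% |
| Sustained | 15%/5% | +0.004 | 91.5% | – |
| Sustained | 25%/15% | −0.010 | 93.5% | – |
| Slight further decline | same losses | at most 0.005 | 86.5–89% | 86–89% |

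Monte Carlo error on coverage at 200 replicates is about √(0.9×0.1/200) = 2.1 points. At Week 48, with 15%/5% early loss, bias was +0.05 log10 and coverage 84%, against 88% without the derived points. Where standard errors were compared they barely changed, so under-coverage comes mainly from bias.

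**The case against.** Much of the case on the other side stands.

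- **Direction.** A reader might infer that the Week 96 bias favours the active arm because HBsAg rebounds off treatment. The documents do not say so. Protocol 2.2.1 and 4.3.1 report declines generally sustained to 16 weeks after the last dose. Protocol 2.1 expects rebound of HBV DNA, not HBsAg, and describes HBsAg loss increasing with time off NA. With a sustained profile the simulated bias nearly vanishes.
- **Exact singularity.** A reader might infer that the unstructured model can never be fitted. That requires EOT to equal Week 48 and EOS to equal Follow-up Week 48 in everyone who has both. Week 48 takes the record closest to Day 337 and EOT the last visit; retests and unscheduled visits can make them differ.
- **Narrow intervals.** A reader might infer that double counting makes the CIs too narrow. The simulations do not show this.
- **The unstructured matrix may fail anyway.** A random intercept plus a full unstructured matrix is not identifiable, and the follow-up windows mix two visit schedules. The fallback exists for such failures, but it changes the covariance and leaves the duplicate records in.
- **Possibly covered elsewhere.** The observed-case rule could be read as stating otherwise, and the Data Presentation Specification, which is not among the documents, may list the MMRM visits. But EOT and EOS are observed records under new labels, so the observed-case wording does not clearly exclude them. Where the SAP wants fewer time points, as for the renal analyses in 6.2.3, it names them.

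**Conclusion.** The point holds as a stated rule that, followed literally, puts duplicate and carried-forward records into the MMRM. This follows from the text and needs no assumption. The consequence for the unstructured matrix is singularity or near-singularity, depending on how many EOT and EOS records differ from the scheduled ones. The uncapped carry-forward is in tension with the SAP's observed-case basis and with its own capped rules.

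Size and direction are conditional on trajectory and dropout, which the documents do not give. Under an assumed HBsAg rebound and 15% to 25% active-arm loss, Week 96 bias is about −0.06 to −0.13 log10 and 90% CI coverage about 63% to 82%. With a sustained profile or about 5% loss the effect is negligible. At Week 48 the shift goes against the active arm. HBV DNA was not simulated.

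If the model covers only the double-blind phase, just the EOT part applies. The analysis is secondary and unadjusted for multiplicity. A reader should not infer any effect on the primary Mantel-Haenszel comparison, which does not use this model.

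**What to change.** Add to SAP 5.3.2.2.1: *Only scheduled post-baseline time points are included; the derived EOT and EOS time points are excluded from the MMRM.* In the same place, name the phase or phases and the visits modelled. Keep EOT and EOS for the descriptive tables.

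This is necessary but may not be enough for the unstructured model to converge. The random intercept should be dropped when an unstructured matrix is used.

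The exclusion costs one SAP sentence. It needs no new data and leaves the primary analysis unchanged.
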